**Table 3: Mean and standard deviation of changes between baseline and 6 weeks by study arm**

	N	Mean	Std. Deviation
True Acupressure	41	-1.9621	2.04466
Sham Acupressure	45	-1.2988	1.63485
Usual Care	51	-0.4336	1.51849
Total	137	-1.1752	1.82757

**Table 4**  
**Multiple Comparisons**

Dependent Variable: Change in BFI between Baseline and week 6 visit

LSD

[figure not shown]
(I) Arm	(J) Arm	Mean Difference (I-J)	Std. Error	Sig.	95% Confidence Interval	
					Lower Bound	Upper Bound
True Acupressure	Sham Acupressure	-0.66329	.37307	.078	-1.4012	.0746
	Usual Care	-1.52851*	.36246	.000	-2.2454	-.8116
Sham Acupressure	True Acupressure	.66329	.37307	.078	-.0746	1.4012
	Usual Care	-.86521*	.35341	.016	-1.5642	-.1662
Usual Care	True Acupressure	1.52851*	.36246	.000	.8116	2.2454
	Sham Acupressure	.86521*	.35341	.016	.1662	1.5642

\*. The mean difference is significant at the 0.05 level.

**Study Limitations and Challenges.** As with any study we anticipate potential barriers. Recruitment may prove to be one potential challenge; however, our methods of recruiting breast cancer survivors from the Michigan Tumor Registry have been effective and we are planning similar methods in this study. We can also recruit from the members of the Michigan Ovarian Cancer Science and Innovation Consortium of which [name] is a member. Attrition from the study may be another challenge. We have had experience in keeping participants in fatigue and cancer studies with higher levels of study burden compared to this proposal for at least 3 months. In our previous studies, which included four in-person visits, twice as many questionnaires, and offered no participant incentives such as a free computer tablet, our withdrawal rates ranged from 10% to 20%. As such, we have planned for a 10% withdrawal rate for this proposal given our lower level of participant burden and greater study incentives.

We also understand that not all women are familiar with or use computers, mobile apps, Wi-Fi or email. This may be a particular concern for older women who will make up a significant portion of the proposed study's participant pool as ovarian cancer rates are highest in women aged 55-64 years with the median age at which women are diagnosed being 63. The most recent PEW statistics on

internet and technology shows that roughly half of all Americans own tablet computers and this has been swiftly rising (see Figure 8). Computer tablet ownership is higher in younger, more educated, white urban adults. Despite this, 37% of adults aged 55-65 and 32% 65+ own a tablet. To address those women who are unfamiliar or have limited familiarity with computer tablets we will provide support from a dedicated research IT personnel [name]. [name] has extensive experience offering computer support to a wide range of computer users of diverse skill sets and sociodemographic backgrounds. We will also supplement [name] support with simple written directions geared to a seventh grade level of education.

**Conclusion.** This proposal aims to investigate a low-cost, evidence-supported intervention for improving fatigue, sleep quality and quality of life in ovarian cancer survivors with persistent cancer-related fatigue. This patient-centered self-management intervention has the potential to be easily disseminated in healthcare settings and

directly to the community via a mobile app. It could also be an adjunct to current treatment options for persistent cancer-related fatigue.

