### **3.2 Randomization.**

The biostatistician will provide sealed envelopes for the randomization of all participants. Participants will be

randomized to one of the three study arms: Acupressure, Sham acupressure or Control. A random generator for block stratified randomization in blocks of 6 participants will be programmed by [name], the study statistician. Eligible patients will be randomized into one of three groups - relaxing acupressure, sham acupressure, or no treatment - in a 1:1:1 ratio for a total of 171 participants with 57 randomized into each group.

We will be delivering our self-acupressure interventions (relaxing and sham) using our modified MeTime Acupressure mobile app. We will rename the MeTime Acupressure app to "Study App" and change the icon so participants will not be able to locate it in the Apple or Google Play Stores and unblind themselves. In association with the 3D Media Lab at the University of Michigan we will create a mobile app for our sham acupressure points. The sham and relaxing acupressure apps will be identical in all aspects except for the acupoint locations. For women randomized into the "no treatment arm" they will receive the acupressure app and AcuWand at the end of their study participation. The acupressure app will be loaded onto computer tablets by our computer information technology (IT) support person. Women in the acupressure arms will also receive an AcuWand to be used in association with the acupressure app to help women apply the correct amount of pressure to acupoints. The women will receive directions within the acupressure app on how to use the AcuWand. The AcuWand has been designed to use two lithium-ion long lasting (up to one year with normal use) batteries. Participants are asked to return the AcuWand with provided materials at no cost to them in order to upload data about frequency, duration and amount of pressure of acupressure applications. Of note: no Wi-Fi connection is needed to use the acupressure app and our IT support person will be available to help participants who are unfamiliar with or have any issues with their tablet, AcuWand or the app.

**Relaxing Acupressure.** There are 5 acupoints with 4 of the acupoints performed on both the left and right sides of the body (total of 9 points to stimulate; see Figure 7). Each of the 9 acupoints will be stimulated for 3 minutes per point

with the AcuWand giving a total treatment time of 27 minutes daily. The relaxation acupoints are:

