### 3.3 Blinding.

Our IT support person will place the computer tablets—already loaded with either the acupressure app--sham or relaxing--or the “no treatment” message and the AcuWands into opaque shipping boxes per our randomization code, i.e., a tablet with the sham acupressure app loaded on it would be placed in a shipping box labeled with a study ID assigned to the sham arm. The outside of the shipping boxes will be labeled with study IDs. This will ensure that only our IT support person will be unblinded, but all study staff and researchers will remain blinded until after the completion of data analyses. The IT support person will not be responsible for collecting or analyzing any study data. Participants in the “no treatment” arm will not be blinded; however, the two self-acupressure arms will be blinded as to which acupressure treatment they have been randomized. The MeTime app will be re-named to “Study App” for the study.

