**Table 2**

	Screening phone call	Baseline Week 0	Treatment Phase Weeks 1 - 6	Follow-up Week 6 (- 2 days/+5 days)	Follow-up Week 12 (- 2 days/+5 days)	Follow-up Week 24 (- 2 days/+5 days)
Phone Screen	X					
Screening Survey	X					
BFI	X	X		X	X	X
PHQ-2	X					
Consent	X					
Pt. Info & Dem.	X					
Concomitant of Medications		X				
Diagnosis & Treatment of initial cancer		X				
FACT-O		X		X	X	X
PSQI		X		X	X	X
PROMIS		X		X	X	X
IPAQ		X				
SCQ		X				
FSQ		X				
MAIA		X		X		
Daily Logbook			X			
Acupressure Fidelity				X		
Assessment of blinding				X		
AcuWand Comfort				X		
Final Evaluation						X

**Administering Study Assessments.** All potential participants will be screened over the phone using a brief questionnaire to confirm eligibility for the study. Enrolled participants will then receive an email link to their RedCAP study measures at baseline, weeks 0, 6, 12 and 24. All the surveys will be administered at all-time points with the exception of descriptive and baseline assessments, which will only be collected at week 0; fidelity, blinding and adherence, which will only be asked at week 6; and a final evaluative questionnaire about the participants' perception of the study and the use of the AcuWand device. Adverse events will be collected at all-time points. Inspirational reminder emails, texts, or phone calls (as appropriate for a given participant) will be made to encourage the highest possible response rate to each round of study assessments. Participants without an email account will be assisted in obtaining a free Gmail account and how to access it on their computer tablet by study staff. Those participants who do not have access to Wi-Fi will be assisted in finding free Wi-Fi in their community (e.g., public library, Starbucks, McDonalds, etc.) IT study staff will be available to assist participants with any questions that may arise. E-mail is required so that study instruments may be accessed through surveys in RedCAP.

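### The one person declared unblinded, the IT support person, is also the on-request helper for women in the two blinded arms, and no safeguard covers what that person may convey to them

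*Combined protocol and SAP*

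**What the plan says.** Section 3.3 (Blinding) describes how tablets carrying the relaxing app, the sham app or a no-treatment message are boxed according to the randomization code. It concludes: "This will ensure that only our IT support person will be unblinded, but all study staff and researchers will remain blinded" until the analyses are finished. One restriction is placed on the role: "The IT support person will not be responsible for collecting or analyzing any study data".

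Section 3.2 (Randomization) gives the same role two further tasks. The first is preparation: "The acupressure app will be loaded onto computer tablets by our computer information technology (IT) support person". The second is participant support: "our IT support person will be available to help participants who are unfamiliar with or have any issues with their tablet, AcuWand or the app".

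Two other places describe IT help in looser terms. Section 4.1, on administering the assessments, says "IT study staff will be available to assist participants with any questions that may arise". Study Limitations and Challenges, in section 9.0, says of women who are new to tablets that "we will provide support from a dedicated research IT personnel". Neither says whether the helper knows the allocation.

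**The concern.** The sham arm exists so that the relaxing versus sham comparison isolates the specific effect of the acupoints (section 4.0). That works only if women in both arms hold similar beliefs about what they received. The primary outcome is the participant's own BFI rating, and the two secondary outcomes, FACT-O and PSQI, are also self-reported, so belief can feed directly into the measurement.

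A helper who knows which app is the sham can convey it without meaning to, through a hesitation, a word of encouragement, or an answer about whether the points are right. Such cues would tend to differ between the arms, and the resulting bias would fall on the contrast that the sham arm was added to support.

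The sponsor already treats participant unblinding as a real threat. Section 3.2 has the app renamed and its icon changed so that women cannot find it in an app store and learn their arm. The support route has no comparable protection.

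**Working it through.** The plan has no figure to reproduce here and no formula applies. The check is a side-by-side reading.

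1. **Who knows the arm.** Section 3.3 states that it is the IT support person and no one else. The knowledge comes from loading the apps (3.2) and packing by the randomization code (3.3).
2. **Who helps participants.** Section 3.2 assigns help with tablet, AcuWand and app to the IT support person, under the same role title and in the same paragraph as the loading task. Sections 3.2 and 3.3 together therefore establish that helper and unblinded person are one role. Section 4.1 and the limitations text are not needed for this step and could not establish it alone.
3. **Who must not know.** Section 3.3 says "the two self-acupressure arms will be blinded as to which acupressure treatment they have been randomized". That is 57 + 57 = 114 planned women. The no-treatment arm is openly unblinded and not at issue.
4. **What each stated safeguard covers.**
   - The bar on collecting or analyzing data protects assessment and analysis.
   - Opaque boxes labelled by study ID protect the other staff.
   - The new app name and icon protect against a search of the app stores.
   - Making the apps identical apart from point locations limits what a woman can infer from her own app.
   - None of these covers what the helper may say to the woman. The plan contains no script, no limit on topics, no contact log and no separate blinded helper.
5. **Whether a leak would be detected.** Table 2 and section 4.1 provide a week 6 question asking which acupressure the woman thought she was doing. It is asked at the primary time point, so it can reveal unblinding but not prevent it. The Statistics Section gives the answer no role in any analysis.
6. **Whether the helper needs to know.** Section 3.2 says the apps differ only in acupoint locations. Technical help with a tablet, an app or the AcuWand does not depend on knowing which set is the sham.
7. **What cannot be worked out.** The documents do not state how many women seek help, when they do so, or how far a cue would move a BFI score.

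**The case against.** The strongest reply is that someone has to load arm-specific tablets. The plan confines the knowledge to one person who assesses nothing, and it tests participant blinding at week 6. That is a reasonable structure and it stands, but it leaves the route from helper to participant open.

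Four stronger readings are tempting, and the documents do not support them.

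- **That all women in both arms are in contact with the unblinded person, during treatment and around the outcome surveys.** Section 3.2 offers help only to those who are unfamiliar with the equipment or have a problem, and gives no timing. Directions within the app (3.2) and written directions (9.0) reduce the need. For the surveys, section 8.0 says they are separate from the app and that a study team member administers them by phone where needed.
- **That section 4.1 and the limitations text identify the unblinded person.** Section 4.1 refers to IT study staff in the context of email, Wi-Fi and survey access. The limitations text concerns familiarity with tablets. Both are supporting text only.
- **That the bias can be sized.** National tablet ownership, quoted in section 9.0, is not a rate of help requests, and any shift per contact would be invented. Table 3 shows how easily this goes wrong: the whole sham versus usual-care difference is 1.2988 − 0.4336 = 0.865 BFI points, so supposing that a support call shifts a sham participant by one point would exceed the entire difference.
- **That neutral codes would make participant-facing staff blind.** Point locations are visible in the app, and under section 4.1 research staff watch women locate their points by Skype at week 6.

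**Conclusion.** The point holds as a gap in design. The plan gives participant support to the only role it declares unblinded, and its one restriction on that role does not protect the participants. The affected comparison is relaxing versus sham on a self-reported primary outcome.

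A reader might infer that blinding was broken or that the estimate is biased by some stated amount. The documents show neither: they show an avoidable risk whose size cannot be derived. The conclusion rests on one assumption, that the role title shared by sections 3.2 and 3.3 denotes the same person or people. Because the remedy is cheap and the exposed contrast is the reason for having a sham arm, the change is worth making.

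**What to change.** Amend section 3.3 in two respects.

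- **Mask the builds.** Supply the two acupressure builds and the packing list to IT under neutral codes (A, B, no treatment). The app developer holds the key and has no participant contact. The 3D Media Lab, which section 3.2 involves in creating the sham app, is a natural holder. The principal investigator, whom section 1.0 credits with developing the MeTime app, is not, since 3.3 keeps researchers blinded.
- **Standardize the support.** Have IT support follow the same script in both acupressure arms, limited to technical help, with no comment on allocation, points or expected benefit. Log each contact by study ID so that contact numbers can later be compared between arms.

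An alternative is to divide the work among existing staff, so that whoever loads and packs tablets does not support participants.

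The cost is a short script, a log and relabelling, with no new staff. The limit is that a helper may still guess the arm from the point locations. The amendment should therefore not claim that no participant-facing person can know the arm, especially given the Skype fidelity check.

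Section 9.2 already reports week 6 changes for 137 participants without naming the study they come from. If they belong to this trial, the amendment can protect only women still to be treated, and the trial report should state who gave support to the others and what that person knew.

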## 10.0 ETHICAL AND REGULATORY CONSIDERATIONS

### 10.1 Institutional Review Board (IRB) Approval

Prior to initiating the study, the PI must obtain written approval to conduct the study from the appropriate IRB. Should changes to study protocol become necessary, protocol amendments will be submitted electronically by the PI or designated study staff to the IRB for approval prior to implementation.

### 10.2 Informed Consent

All potential candidates for the study will be given an electronic copy of the study informed consent to read. The investigator or their designee will explain all aspects of the study in lay language and answer all the candidate's questions regarding the study. If the candidate decides to participate in the study, they will be asked to sign the informed consent document electronically. Participants who refuse to participate or who withdraw from the study will be treated without prejudice.

The informed consent document must be reviewed and approved by the IRB prior to study initiation. Any subsequent changes to the informed consent must be approved by the IRB for approval prior to implementation.

### 10.3 Data and Safety Monitoring

#### 10.3.1 Guidelines

The purpose of the data and safety monitoring plan is to insure the safety of participants, the validity of data, and the appropriate termination of studies for which significant benefits or risks have been uncovered or when it appears that the trial cannot be concluded successfully. Risks associated with participation in research must be minimized to the extent practical, and the method and degree of monitoring should be commensurate with risk. The essential elements of the Data and Safety Monitoring Plan include:

- Monitoring the progress of trials and the safety of participants
- Plans for assuring compliance with requirements regarding the reporting of adverse events (AE)
- Plans for assuring data accuracy and protocol compliance.

The known or expected risks associated with this study include:

- Risk of bruising at points of pressure; there is a very small chance (<1%) of having bruises at points of pressure if too much pressure is applied. This bruising should not continue or get worse. To minimize the risk of bruising study staff members will demonstrate the correct amount of pressure to apply at the start of the study. Additionally, a member of the research team will call participants during the study to evaluate their health and safety. During these conversations study team members will ask about any bruising.
- Risk of breach in confidentiality; there is a possible risk of the loss of confidentiality of participant medical information. The study team will try to protect participant privacy and the confidentiality of information.

#### 10.3.2 Study-Specific DSMP

This study will be monitored in accordance with the NCI approved University of Michigan Rogel Cancer Center Data and Safety Monitoring Plan.

The study team will meet every six months or more frequently depending on the activity of the protocol. The

discussion will include matters related to the safety of study participants (SAE/UaP reporting), validity and integrity of the data, enrollment rate relative to expectations, characteristics of participants, retention of participants, adherence to the protocol (potential or real protocol deviations) and data completeness. At these regular meetings, the protocol specific Data and Safety Monitoring Report form will be completed and signed by the Principal Investigator or by one of the co-investigators.

Data and Safety Monitoring Reports will be submitted to the University of Michigan Rogel Cancer Center Data and Safety Monitoring Committee (DSMC) every six months for independent review.

#### **10.4 Record Retention**

Clinical records for all participants studied, including CRFs, history and physical findings, laboratory data, and results of consultations, will be maintained by the Investigator in a secure storage facility and stored for at least five years after the study is closed.

